### 11.6.3 Subject Disposition

The number of patients screened, randomized, withdrawn, and included in each analysis population (ITT, Per Protocol) will be reported by treatment group and according to site. In addition, the number of patients completing this trial and the reasons for patient withdrawal will be tabulated by treatment group. These data will be used to prepare a CONSORT diagram.

#### **11.6.4 Baseline (Pre-Treatment) Analyses**

Demographic and baseline clinical characteristics will be presented by treatment group for all patients. For categorical variables we will report frequencies and percentages. For continuous variables we will report means and standard deviations.

#### **11.6.5 Concomitant Medication Use**

We will report the incidence of concomitant medication use according to treatment group using the ITT population.

### **11.7 Efficacy Analyses**

#### **11.7.1 Primary Efficacy Analysis of the Primary Efficacy Endpoint**

We present compelling preliminary data and extensive literature suggesting that the effect of antimicrobial therapy is likely to differ in certain subgroups of children with acute sinusitis. Accordingly, the primary efficacy analysis will assess the heterogeneity of treatment effect in subpopulations defined by presence of nasopharyngeal colonization and by the presence of colored nasal discharge (i.e., to test for interaction between treatment and subgroup effects).

Interactions between treatment group and each subgrouping variable will be tested simultaneously. A Generalized Estimating Equations (GEE) model will be fit by including treatment by subpopulation interaction terms (adjusted for the baseline PRSS score) using the ITT dataset (see Section 6.8 for detailed multiple testing procedure). The regression analysis will be adjusted for clinical site as a potential confounding factor.

Assumptions required for the validity of GEE will be assessed. These will include (i) the marginal mean of the response depends on a link function, (ii) the marginal variance depends on the marginal mean, and (iii) the correlation within subject depends on the marginal mean and other parameters. Therefore an appropriate link function will be chosen for the primary outcome and the goodness of fit of the model will be assessed.

#### **11.7.2 Secondary Efficacy Analysis of the Primary Efficacy Endpoint**

The secondary efficacy analysis will compare the PRSS scores during the first 10 days of therapy in the two treatment groups. This analysis is considered secondary because reporting the average treatment effect in the entire sample is not appropriate if the treatment effect in the subgroups we are considering is heterogeneous. GEE will be used to compare the marginal means adjusted for the baseline PRSS score and stratification variables using the ITT population.

In addition, we will explore whether heterogeneous response to treatment is observed for other baseline variables, including worsening presentation, age, history of allergic rhinitis, and individual pathogens. We consider this investigation of the additional variables to be only

exploratory, possibly providing information that may prove important in conducting future studies.

### **11.7.3 Secondary Efficacy Analyses of the Secondary Endpoints**

Secondary efficacy variables include treatment failure, development of AOM, and receipt of an antibiotic. All of these are dichotomous variables. We will use the Cochran-Mantel-Haenszel test stratified by study site, using the ITT dataset.

Additional analyses of the dichotomous secondary efficacy variables will use logistic regression to adjust for baseline covariates and other prognostic variables.

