## PROTOCOL SUMMARY

Title:	Efficacy of Antibiotics in Children with Acute Sinusitis: Which Subgroups Benefit?
Phase:	III
Objectives:	
Primary
 
 
To determine whether the effect of antimicrobial treatment differs in predefined subgroups of children with acute sinusitis (i.e., to test for treatment subgroup interactions). Subgroups will be defined by the (1) presence vs. absence of nasopharyngeal (NP) colonization with respiratory pathogens (Streptococcus pneumoniae, Haemophilus influenzae, or Moraxella catarrhalis), and (2) presence vs. absence of colored (yellow or green) nasal discharge.
 
 
Secondary
 
 
To determine whether antimicrobial therapy is superior to placebo (i.e., to test for the overall effect).
 
 
Tertiary
 
 
To evaluate compliance with study product.
 
To assess adverse events associated with use of amoxicillin clavulanate, including the development of bacterial resistance.
 
To compare resource utilization according to treatment strategy.
 

Population:	688 children aged 2 to 12 years, who meet the current AAP criteria for sinusitis.
Inclusion Criteria:	2 -12 years of age (before 12 th birthday); Persistent sinusitis: URI symptoms present for >10 days without improvement (11-30 days); Worsening sinusitis: URI symptoms worsening after a period of improvement (6-10 days); baseline score $\geq 9$ on the Pediatric Rhinosinusitis Symptom Scale (PRSS), $\geq 2$ doses of pneumococcal conjugate vaccine or appropriate for age.
Exclusion Criteria:	Sinusitis with severe presentation ( $\geq 3$ days of colored nasal discharge and fever $\geq 39^\circ$ C); asthma/allergic rhinitis explains symptoms; allergy to amoxicillin-clavulanate; immotile cilia syndrome; cystic fibrosis; immunodeficiency; parental/legal guardian inability to read/write English or Spanish; other concurrent infection (e.g., pneumonia, acute otitis media, streptococcal pharyngitis); systemic toxicity; wheezing on exam; antibiotic use within 15 days; prior sinus surgery;
Number of Sites:	5 sites (Pittsburgh will enroll 388 children, and Bardstown, and Madison will enroll 100 children each).. At each site, patients will be enrolled from primary care clinics.

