#### Identification of important prognostic factors

We compared median time to resolution of symptoms (defined as reaching a score of  $\leq 2$  on the PRSS on two successive occasions) according to the levels of the potential prognostic factors (variables measured at baseline) using a proportional-hazards model in children receiving antimicrobial therapy for acute sinusitis. The only variable that remained independently associated with time to resolution after adjustment for baseline severity of symptoms was nasopharyngeal colonization with pathogens (*S. pneumoniae*, *H. influenzae*, *M. catarrhalis*) at baseline. Median time to symptom resolution in those with and without nasopharyngeal colonization with pathogens was 7.5 and 8.5 days, respectively ( $p=.008$ ). In contrast, in two previous studies of children with URI who were not receiving antimicrobial therapy, the presence of pathogens predicted *slower* resolution of symptoms. Together, these findings suggest that in this trial, children who are colonized with pathogens will respond differently to treatment than those who are not colonized with pathogens (i.e., heterogeneity of treatment effect). Our preliminary data, which are similar to the data from Kaiser, suggest that testing for bacteria in the nasopharynx may assist greatly in identifying children who will respond to treatment with antibiotics. If we find that only those children colonized with pathogens benefit from antimicrobial therapy, then the management of children with suspected sinusitis could be similar to the management of children with streptococcal pharyngitis. A rapid antigen test for *S. pneumoniae* is commercially available, can be performed at the bedside, and has good accuracy (sensitivity 88 to 92%, specificity 95 to 97%). Similar PCR-based tests for *H. influenzae* and *M. catarrhalis* have also been developed. By prescribing antimicrobials only to those with pathogens, antimicrobial prescribing could be sharply reduced. Of note, in our preliminary dataset, results were driven largely by the subgroup of children colonized with *S. pneumoniae*. We suspect that this was due to the smaller number of children colonized with *H. influenzae* and *M. catarrhalis*. The ability of the PRSS scale to discern differences in time to resolution according to the presence or absence of pathogens in the nasopharynx further supporting its utility and validity. In summary, our preliminary study supports using the presence of pathogens

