#### 3.2.2 Secondary Outcome Measures

##### Secondary Efficacy Outcomes

- 1) Treatment failure – Children who are not improving at the expected rate will be identified through daily monitoring of PRSS scores. These children will be seen by the study team and rescue medication will be prescribed as clinically indicated. We will define treatment failure as follows:
  - a. Worsening at any time—PRSS score increased by >20% from entry.
  - b. No change by 48 hours—PRSS score decreased by <2 points from entry (Day 1) to Day 3.
  - c. Failure to improve significantly by 72 hours—PRSS score decreased by <20% from entry (Day 1) to Day 4.
  - d. PRSS decreased by <20% from enrollment on 2 consecutive occasions Days 5-11
  - e. Still symptomatic (PRSS score  $\geq$ 50% of entry score) at the time of the end-of-study follow-up visit (Days 12 to 18).

This definition is similar to that used by clinicians in practice. A similar composite outcome was used successfully in previous studies by [name]. Days 3 and 4 were chosen as decision points because most (>90%) treatment failures are expected to occur around that time. A 20% change was chosen because this represents the smallest change that appears to be clinically meaningful (see Table 1). Using these definitions, we estimate, based on our preliminary data and on the failure rates observed in previous studies using the same antibiotic, that the rate of treatment failure in the antibiotic arm will be approximately 15%.

- 2) Development of AOM (acute symptoms and a bulging tympanic membrane) on Days 1 to 11.
- 3) Receipt of an antibiotic (other than the assigned study medication) on Days 1 to 11 for any indication.

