#### 5.3.1 Randomization Procedures

Randomization will occur in blocks of 4 and investigators and participants will be masked to treatment allocation. Stratification will be based on the presence/absence of colored (yellow or green) nasal discharge and site of enrollment.

High-dose amoxicillin-clavulanate potassium (90/6.4 mg/kg/day, maximal dose: 4 g/day, Teva Pharmaceutical Industries LTD., see Other Attachments section for product insert) or placebo

will be administered twice daily for 10 days. Placebo for all study sites will be prepared centrally by a research pharmacist at the University of Pittsburgh Medical Center Investigational Drug Service (IDS). The IDS is well suited to this task because it is currently preparing the same placebo (for amoxicillin-clavulanate) for our multicenter NIAID-sponsored AOM study (BAA-NIAID-DMID-NIHAI2009058). All study medications will be packaged in containers of identical appearance and will be labeled with a unique number. The IDS will maintain drug accountability records for all participating sites.

Per International Council for Harmonization (ICH) guidelines, screening records will be kept at each participating clinical study site to document the reason why an individual was screened but failed trial entry criteria.

All study personnel except the research pharmacist at the UPMC Investigational Drug Service will be masked to treatment group assignment. The subjects and parents/legal guardians of study subjects will also be masked to treatment group assignment. Randomization codes will not be broken until completion of the trial. Only in the event of a medical emergency and if unmasking would change the selection of treatment, will subject treatment assignment be revealed. The ISM or PI may unmask the treatment for a subject by contacting the Research Pharmacist at the UPMC Investigational Drug Service. Unmasked subjects will complete any remaining protocol assessments (diaries and routine end-of-study follow-up visit). When considering unmasking treatment for a subject, the investigator should consider whether knowing the identity of the treatment would change the selection of treatment. If knowledge of the subjects' treatment assignment would not affect treatment decisions, unmasking will not occur.

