## 11 STATISTICAL CONSIDERATIONS

### 11.1 Study Hypotheses

Hypothesis 1: Children not colonized with respiratory pathogens are unlikely to benefit from antimicrobial therapy.

Hypothesis 2: Children without colored nasal discharge are unlikely to benefit from antimicrobial therapy.

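### Randomization is stratified by site and colored discharge, but the main test of the binary secondary endpoints stratifies by site only: valid, slightly conservative if color predicts outcome, and easily aligned

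*Combined protocol and SAP*

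**What the plan says.** - **Randomization (Section 5.3.1):** "Stratification will be based on the presence/absence of colored (yellow or green) nasal discharge and site of enrollment", in blocks of 4 with 1:1 allocation.
- **Binary secondary endpoints (Section 11.7.3):** treatment failure, acute otitis media and receipt of another antibiotic are compared with a CMH test "stratified by study site, using the ITT dataset". Additional analyses "will use logistic regression to adjust for baseline covariates and other prognostic variables", but the covariates are not named.
- **Overall PRSS comparison (Section 11.7.2):** the GEE model is "adjusted for the baseline PRSS score and stratification variables using the ITT population".
- **Compliance (Section 11.10.1):** also a CMH test by site only, so the plan is consistent across its CMH tests. The mismatch is with the randomization and with Section 11.7.2.
- **Site pooling (Section 11.6.1):** small sites may be pooled before unblinding.

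**The concern.** Blocking on color makes the arms nearly equal in their share of children with colored discharge. If color also predicts failure, that balance reduces the true sampling variance of the treatment difference. A test that ignores color still estimates the variance as if color could differ by chance between arms. Its standard error is then slightly too large, so the actual type I error falls below 5% and some power is lost.

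The direction is safe: there is no bias and no inflated error. At stake is a small amount of efficiency on three secondary endpoints. There is also an unexplained difference between two neighboring sections in how they treat the stratification factors. The logistic regression in Section 11.7.3 does not settle this, because it is supplementary and does not commit to including color.

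**Working it through.** **No plan figure to reproduce.** The documents give no power or sample size for the CMH tests. The total of 688 (344 per arm) comes from the interaction test in Section 11.11 and is unaffected.

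**Inputs from the documents**
- N = 688, 1:1, blocks of 4 within site by color; two-sided 0.05.
- Section 3.2.2 expects "that the rate of treatment failure in the antibiotic arm will be approximately 15" percent.
- Site sizes: the Protocol Summary says "Pittsburgh will enroll 388 children, and Bardstown, and Madison will enroll 100 children each". That accounts for 388 + 100 + 100 = 588 of 688 children. Five sites are stated, but Section 4 lists four.

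**Assumptions, not in the documents**
- Placebo failure 23.5%.
- 40%, 60% or 80% of children with colored discharge.
- Color-outcome odds ratio (OR) 1, 2 or 3.
- Four sites of 388/100/100/100 or five of 388/75/75/75/75.

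**Step 1: power without a color effect, by formula.** With p1 = 0.235, p2 = 0.15, n = 344 per arm and mean rate 0.1925:
- null SE = √(2 × 0.1925 × 0.8075 / 344) = 0.03006
- alternative SE = √((0.235 × 0.765 + 0.15 × 0.85) / 344) = 0.02989
- power = Φ((0.085 − 1.96 × 0.03006) / 0.02989) = Φ(0.873) = 80.9%

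**Step 2: conservatism, by formula.** Let c be the share with colored discharge, and p_c and p_n the failure rates with and without it. Ignoring color, the per-child variance is p̄(1 − p̄). With color balanced by design, the relevant variance is p̄(1 − p̄) − c(1 − c)(p_c − p_n)². The actual type I error is therefore about 2[1 − Φ(1.96/√r)], where r is the second variance divided by the first.

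Example with p̄ = 0.15 in both arms, c = 0.4 and OR 3:
- p_c = 0.2354 and p_n = 0.0931
- between-color variance = 0.24 × 0.1423² = 0.00486
- r = (0.1275 − 0.00486) / 0.1275 = 0.962, and √r = 0.981
- type I error = 2[1 − Φ(1.998)] = 4.6%

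At OR 2 and c = 0.4, r = 0.985 and the type I error is 4.8%.

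**Step 3: simulation.** 200,000 trials per scenario, CMH without continuity correction. The standard error is at most 0.02 points for a power difference and 0.05 points for a type I error.

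Power (%), site only → site by color, four sites:

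| Colored | OR 1 | OR 2 | OR 3 |
|---|---|---|---|
| 40% | 81.1 → 81.1 | 81.4 → 81.9 | 81.6 → 82.8 |
| 60% | 80.9 → 80.9 | 81.2 → 81.7 | 81.6 → 82.5 |
| 80% | 81.0 → 81.0 | 81.2 → 81.4 | 81.3 → 81.8 |

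With five sites, the gains in points at OR 1/2/3 are 0.01/0.48/1.17 (40%), 0.01/0.40/0.93 (60%) and −0.01/0.24/0.48 (80%).

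Type I error (%) at 15% failure in both arms, site only vs site by color:

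| Colored | OR 2, four sites | OR 2, five sites | OR 3, four sites | OR 3, five sites |
|---|---|---|---|---|
| 40% | 4.7 vs 4.9 | 4.8 vs 4.9 | 4.6 vs 5.0 | 4.5 vs 4.9 |
| 60% | 4.8 vs 4.9 | 4.9 vs 5.1 | 4.7 vs 5.0 | 4.6 vs 5.0 |
| 80% | 5.0 vs 5.1 | 4.9 vs 4.9 | 4.8 vs 5.0 | 4.8 vs 5.0 |

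These agree with the formulas in steps 1 and 2.

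**Step 4: the trial's own hypothesis.** Hypothesis 2 in Section 11.1 reads "Children without colored nasal discharge are unlikely to benefit from antimicrobial therapy". Taking 30% vs 15% failure (placebo vs antibiotic) in colored-discharge children and 15% in both arms otherwise, four-site power is 53.7 → 54.0% (40% colored), 85.0 → 85.2% (60%) and 97.5 → 97.5% (80%).

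**Step 5: stronger effects.** A separate run used 24% vs 15% failure, 50% colored, four sites and 20,000 trials per scenario. It gave 85.2 → 85.2% at OR 1, 85.7 → 86.0% at OR 2, 85.3 → 86.1% at OR 3 and 86.0 → 87.9% at OR 5. With 30% failure in both arms, site-only type I error was 4.0% at OR 3 and 3.6% at OR 5, against 4.7% and 4.8% with color included.

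**Step 6: does adding color hurt when events are rare?** At assumed event rates of 2%, 3% and 5%, type I error is 4.7–5.0% for both tests. At 3% vs 8% with no color effect, both tests have the same power: 83.6% with four sites and 83.8% with five.

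**The case against.** The strongest reply is that nothing here is wrong. A pre-specified, site-stratified CMH test is legitimate, and the gain depends on an association the documents never report. The nearest evidence, in Section 2.1.3 (treated children, outcome time to resolution), points the other way: "The only variable that remained independently associated with time to resolution after adjustment for baseline severity of symptoms was nasopharyngeal colonization with pathogens". Colored discharge is linked there to pathogens and radiographs, not to outcome. At an OR of 1.5 the gain is only 0.0 to 0.2 points, and under Hypothesis 2 it is 0.0 to 0.3. Section 11.7.2 itself regards the overall average as inappropriate if subgroup effects differ, so a sharper pooled test matters least in that case. The logistic regression may include color anyway. Finally, Section 14.2 requires protocol amendments to be approved and sent to the IRBs, which is more than a line of text.

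Most of this stands as a statement of size: the gain is small and may be zero. The amendment procedure is a real cost if the change is made alone. None of it shows a statistical disadvantage in analyzing by the strata used to randomize. The unnamed logistic covariates neither commit to color nor replace the main test.

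**Conclusion.** The point holds as a minor, optional improvement. The main CMH test omits one of the two randomization factors. It remains valid, and it is slightly conservative if color predicts outcome. Up to an odds ratio of 3, the loss runs from nothing to about 1.2 power points, and site-only type I error at 15% failure is 4.5–5.0%. These sizes rest on an assumed placebo failure rate, color prevalence, color-outcome association and site layout; only the 15% antibiotic-arm rate is the plan's. Four and five sites give the same picture. The primary interaction analysis and the sample size are untouched.

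**What to change.** In Section 11.7.3, state that the CMH test is stratified by site (after any pooling under Section 11.6.1) crossed with colored discharge as recorded for randomization. Sections 11.7.1 and 11.10.1 need no change on this account.

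The change is one sentence and needs no new data, because color must be known for every child before randomization. The number of strata doubles, to 8 with four sites or 10 with five. Because the section is part of the protocol, the change falls under the amendment procedure in Section 14.2. It is best carried with another amendment and settled before unblinding.

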## **11.8 Missing Data**

For children with missing values for the primary endpoint (no diary data available for a particular day), we will use only the days with non-missing values, which can be accommodated by the GEE method. Children with no diary entries will be excluded from the analysis. If a patient has missing data for a dichotomous secondary outcome variable, we will perform a sensitivity analysis first assuming that all such patients had the deleterious outcome (for instance, treatment failure) and then assuming that all such patients had a favorable outcome.

The proportion of patients with missing data for each outcome variable will also be compared between treatment groups and the sensitivity to the missing data will be examined by reanalyzing the outcome using only the non-missing data. However, we are confident that the amount of missing data will be negligible because study procedures have been put in place to minimize missing data.

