Availability of Subjects:	Based on the preliminary data presented, we will be able to recruit at least 100 patients per year in Pittsburgh alone. Likewise, based on the strong track record of enrollment in clinical trials, other sites will be able to recruit at least 25 patients per year during the course of the study.
Consent Process:	Parents/legal guardians of children who meet criteria for persistent or worsening presentations of acute sinusitis will be approached for informed consent. Assent will be sought from older children who are believed to be developmentally capable.

Retention and Follow-up:	In a preliminary study, our retention rate was 94%. In this study, we have built in additional measures to improve retention (electronic daily diary, phone calls to patients with missing data, reimbursement for completing the diary, and home visits). We anticipate no changes in the approaches for retention during the course of the trial.
Study Duration:	5 years
Subject Duration:	12 to 18 days
Description of Agent and Rationale:	Amoxicillin-clavulanate (90/6.4 mg/kg/d in 2 divided doses for 10 days) or matching placebo will be used. Amoxicillin-clavulanate was chosen because of the increasing prevalence of H. influenzae in nasopharyngeal specimens of children with bacterial respiratory infections, and because it is the most effective available orally administered antimicrobial drug against the respiratory pathogens most commonly causing sinusitis. A high dose of amoxicillin will minimize the number of children experiencing treatment failure in the active treatment group. The use of an agent with suboptimal antibacterial coverage would also make it more difficult to determine whether treatment effect heterogeneity exists. Ten days was chosen because this is the duration most frequently used in practice.

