## 4 STUDY DESIGN

This is a large, multi-center, randomized, double-blind, placebo-controlled, parallel group trial comparing antimicrobial treatment with amoxicillin-clavulanate potassium with matching placebo in children aged 2 years through 12 years of age, who meet the current AAP criteria for sinusitis. (See Schematic of Study Design).

Participants will be recruited from the primary care clinics at 5 sites: (1) Children's Hospital of Pittsburgh of UPMC and its affiliated Pediatric PittNet Practice Based Research Network (PBRN), CCP South Hills Pediatric Associates and CCP HealthQuest Hampton, Pittsburgh (Site PI and study Co-PI: [name]); (2) Kentucky Pediatric and Adult Research, Bardstown, KY (Site PI: [name]); (3) University of Wisconsin, Madison, WI (Site PI and Study Co-PI: [name]) and (4) Cyn3rgy Research (Site PI: [name]).

Children will be randomized 1:1 to receive treatment for 10 days with either twice daily amoxicillin-clavulanate or matching placebo. Randomization will occur in blocks of 4 and study participants and study personnel (except the research pharmacist) will be masked to treatment allocation. Stratification will be based on the presence/absence of colored (yellow or green) nasal discharge and site of enrollment. Randomization codes will not be broken until completion of the trial unless there is a medical emergency that necessitates unmasking. A total of 688 children (approximately 344 in each treatment group), who meet the current AAP criteria for sinusitis will be enrolled over a 5-year period. Each participant will be followed for 12 to 18 days. Antimicrobial therapy will consist of amoxicillin-clavulanate suspension, 90 mg/kg/day divided into two equal doses. The placebo will be nearly identical in color, taste, and consistency to amoxicillin clavulanate. Amoxicillin clavulanate suspension will be purchased (Augmentin® Pediatric Suspension from Teva Pharmaceutical Industries Ltd.) and rebottled by the University of Pittsburgh Medical Center Investigational Drug Service (IDS). Both Amoxicillin clavulanate and placebo will be similarly labeled with a code number that masks site investigators, site staff, parents/legal guardians and children to the formulation. Study medication will be distributed to clinical sites by the IDS.

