## 11.11 Sample Size Justification

To estimate the sample size for this trial, we used estimates of within-subject correlation and grand variance from our preliminary data of children diagnosed with acute sinusitis. Because two simultaneous tests for interactions are being conducted, we used a two-sided significance level of 0.025 (50:50 split of the overall significance level of 0.05 for Bonferroni adjustment).

Assuming an  $\alpha$  of 0.025 (two-sided test), 344 evaluable children per treatment group will provide statistical power of 80% to detect an interaction effect size of 2.5 points in the mean symptom score (as measured by the PRSS) over the 10-day period assuming, as per results presented in Leon and Heo, that the required sample size to detect an interaction between treatment group and a subgroup would be four times that of a main effect of the same magnitude for a repeated measures outcome under a 2x2 factorial design.

Even though we have calculated the sample size using the simple Bonferroni procedure, for the final analysis we will use a modified Bonferroni procedure for multiple testing, which is not as conservative for highly correlated test statistics. Under the Simes' procedure, the null hypothesis associated with the smallest p-value will be rejected if the p-value is smaller than or equal to  $\alpha / 2$  and one associated with the second smallest p-value will be rejected if the p-value is smaller than or equal to  $\alpha / 2$ . Here  $\alpha / 2$  is the appropriate significance level for the interim or definitive analysis. Specifically, the (ordered) observed p-values will be compared using 0.0025 and 0.005 for the interim analysis and using 0.024 and 0.048 for the definitive analysis.

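### The missing-data checks for the binary secondary outcomes never vary the outcome by arm, so they can miss fragility when missingness is similar across arms or higher on placebo

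*Combined protocol and SAP*

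**What the plan says.** Section 11.7.3 names three dichotomous secondary efficacy variables (treatment failure, AOM, receipt of an antibiotic) and tests them in the ITT set with a Cochran-Mantel-Haenszel test stratified by site.

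For children whose value is missing, Section 11.8 says "we will perform a sensitivity analysis first assuming that all such patients had the deleterious outcome (for instance, treatment failure". The second run reverses that assumption: "then assuming that all such patients had a favorable outcome". The instruction covers every such child and makes no distinction by arm.

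The section adds two further checks. One looks at how much is missing in each arm: "The proportion of patients with missing data for each outcome variable will also be compared between treatment groups". The other is a complete-case run, in which "sensitivity to the missing data will be examined by reanalyzing the outcome using only the non-missing data". It gives no expected amount of missing data, saying only that "we are confident that the amount of missing data will be negligible". Nowhere do the documents specify an opposite-arm scenario, a tipping-point analysis or multiple imputation for these outcomes.

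**The concern.** An all-bad run followed by an all-good run looks like a lower and an upper bound. For a comparison between arms it need not be one, because the same value goes into both arms and largely cancels. The risk to the comparison is that missing children on antibiotic fared differently from missing children on placebo, and neither run represents that.

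Such a difference is plausible here. Section 2.3.1 reports diarrhea in about a third to a half of children taking the active drug, so children could drop out for different reasons in the two arms even if the numbers match.

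At stake is how far a positive secondary result can be trusted. Two nearly identical sensitivity results could be read as reassurance about a departure that was never tested.

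**Working it through.** **Plan's own figure.** The documents give no figure for this sensitivity analysis, so there is none to reproduce. The 344 per arm is taken from Section 11.11 ("344 evaluable children per treatment group will provide statistical power of 80% to detect an interaction effect size of 2.5 points") and serves only as an arm size. It cannot be rederived, because the SD and within-subject correlation are not reported, and the point does not depend on it.

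**Inputs from the documents.** 344 per arm, 1:1 (Sections 4 and 11.11); about 15% failure on antibiotic (Section 3.2.2); two-sided 0.05 (Section 11.6.1).

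**Assumptions.** Placebo failure of 23%, 25% or 30% (not stated in the plan). Missing 6% (21 per arm, by analogy with the 94% retention of the preliminary study in the Protocol Summary) or 2% (7 per arm). P values are from an unstratified chi-square, a stand-in for the site-stratified test.

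**Formula.** Let p be the observed failure rate, m the missing fraction and q the failure rate among missing children, with T for antibiotic and C for placebo. The difference, placebo minus antibiotic, is

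D = pC(1 - mC) - pT(1 - mT) + mC·qC - mT·qT.

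- All favorable (qT = qC = 0): D = pC(1 - mC) - pT(1 - mT).
- All deleterious (qT = qC = 1): the same plus (mC - mT).
- Opposite-arm worst case (qT = 1, qC = 0): the all-favorable value minus mT.
- Complete case: pC - pT, which amounts to q = p within each arm.

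If mT = mC = m, both planned runs equal (1 - m)(pC - pT), and the worst case is that value minus m.

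**Worked case, 15% v 25%, 21 missing per arm.** 323 are observed per arm. Failures: 0.15 × 323 = 48.45 and 0.25 × 323 = 80.75.

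- All deleterious: 69.45/344 = 20.2% v 101.75/344 = 29.6%; 9.4 points, p=0.004.
- All favorable: 14.1% v 23.5%; 9.4 points, p=0.002.
- Worst case: 20.2% v 23.5%; 3.3 points, p=0.30.
- Opposite corner: 14.1% v 29.6%; 15.5 points, p<0.001.

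**Range, equal missingness.**

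| Missing per arm | Placebo rate | Both planned runs | Worst case |
|---|---|---|---|
| 6% | 23% | 7.5 (p=0.021, 0.010) | 1.4 (p=0.65) |
| 6% | 25% | 9.4 (p=0.004, 0.002) | 3.3 (p=0.30) |
| 6% | 30% | 14.1 (both p<0.001) | 8.0 (p=0.015) |
| 2% | 23% | 7.8 (p=0.011, 0.008) | 5.8 (p=0.055) |
| 2% | 25% | 9.8 (p=0.002, 0.001) | 7.8 (p=0.012) |
| 2% | 30% | 14.7 (both p<0.001) | 12.7 (p<0.001) |

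**Unequal missingness, 15% v 25%, counts rounded to whole children.**

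- More missing on placebo (14 antibiotic, 28 placebo; observed failures 50 and 79). All deleterious: 64/344 v 107/344, 12.5 points. All favorable: 50/344 v 79/344, 8.4 points. Worst case: 64/344 v 79/344, 4.4 points (p=0.16). The planned runs miss it.
- More missing on antibiotic (28 and 14; observed failures 47 and 82). Complete case: 10.0 points (p=0.0015). All deleterious: 75/344 v 96/344, 6.1 points (p=0.064). Here the planned run does show fragility.

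**Rare outcome, assumed AOM 1% v 4%, 21 missing per arm.** Observed 3/323 v 13/323: 3.1 points (p=0.011). All deleterious: 24/344 v 34/344, 2.9 points (p=0.17). The difference barely moves, but significance is lost through added noise.

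**The case against.** A reader might infer that the planned check can never show a result to be fragile, or that the trial would report robustness whatever the truth. The documents do not support either. With more missing on antibiotic, the all-deleterious run can lower the difference substantially, and with a rare outcome significance can go even under equal missingness. Section 11.8 also commits to no conclusion about robustness.

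Nor are the two imputation runs the only checks. Comparing missing proportions shows whether missingness is in fact similar by arm, which is the condition that matters most here. What it cannot show is how the missing children fared, and the complete-case reanalysis simply assumes that they resemble the observed children in their own arm.

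Missing data may also be well below 6%. The 94% is retention in an earlier study, and the Protocol Summary lists added retention measures. Missed diaries are followed up the next morning (Sections 4 and 7.3), and final-visit data may be obtained at home or by phone or email (Section 7.4). Any one of five criteria makes a failure, and Section 3.2.2 expects over 90% of failures around Days 3 and 4, so a child lost later may already be classified. Children with no diary entry are outside the ITT set. At 2% or 3% missing (7 or 10 per arm), 15% v 25% survives even the worst case (p=0.012 and 0.028).

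That limits the size of the problem without removing it: at 2% missing, 15% v 23% gives planned p values of 0.008 and 0.011 against a worst case of 0.055. The worst case is an extreme (every missing child fails in one arm, none in the other) and is a bound, not a forecast.

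**Conclusion.** The point holds as a gap in the sensitivity analysis. No check in Section 11.8 varies the outcome among missing children separately by arm. With equal missingness the two imputation runs coincide on the risk-difference scale and bracket nothing; with similar missingness, or more on placebo, they can miss fragility.

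The equal-missingness result is algebra and needs no assumption about rates. How much it matters rests on assumed placebo rates and missing fractions: across the table, the worst case falls below the planned runs by about 2 points at 2% missing and about 6 points at 6% missing. Whether that overturns a result depends on the observed difference; 15% v 30% stays significant in every balanced case shown.

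The scope is the three binary secondary outcomes. The primary PRSS interaction tests use GEE on available days and are unaffected. This is a worthwhile, inexpensive improvement to the plan and not an error in it.

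**What to change.** In Section 11.8, before unblinding, add a tipping-point analysis for each binary secondary outcome. Vary the event rate among missing children from 0 to 1 separately in each arm, repeat the site-stratified Cochran-Mantel-Haenszel test at each grid point, and report where the conclusion changes. Include the two opposite-direction corners (missing antibiotic = event with missing placebo = no event, and the reverse), labelled as bounds. Keep the two same-outcome runs, the complete-case reanalysis and the comparison of missing proportions as reference points.

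The cost is a few lines of SAP text and brief programming on data already collected, with no change to trial conduct. The drawback is that the corners are deliberately extreme: they must be reported as bounds and not as plausible estimates, or a sound result could be made to look weak.
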